Subjects will continue to count carbohydrates for all meals and snacks and enter this amount into the controller of the closed-loop system. For youngest age group (<8 y), manual pre-meal boluses may not necessarily be given, at discretion of the investigator, to test the robustness of the system. Subjects will not utilize "correction doses" for hyperglycemia except if instructed by study staff.

5) Hypoglycemia and Hyperglycemia Management

Subjects and parents will be instructed to test BG on the study meter for any CGM readings under 70 mg/dL or if subject develops symptoms of hypoglycemia. For any documented BG <70 mg/dL or in the setting of symptoms of hypoglycemia, study staff will be alerted, subject will be treated with 15-30 gm rapid-acting carbohydrate (such as juice or glucose tabs), and BG will be rechecked in 15 minutes. Additional treatments for hypoglycemia will be given every 15 minutes as needed until BG levels are \geq 70 mg/dL. For CGM readings \geq 300 mg/dL for > 1 hour, subject will test BG, and if confirmed BG \geq 300 mg/dL, subject will test blood ketones. Subject or parent will contact investigator for any blood ketone level $>$ 1.0 mmol/l for instructions on supplemental insulin,

changing insertion site, and continuation of closed-loop control, as per the Treatment Protocol (Table 1).

6) Remote Monitoring

Subjects' parent/guardian and study staff will receive event-based SMS (text) alerts on their cell phones for low sensor readings, or for other operational issues affecting performance of the system. For these studies, the threshold for predictive hypoglycemia alerts will be set to 65 mg/dL. If the hypo- alert is activated, subjects will be required to test BG and communicate result to study staff. If study staffs have received an SMS alert, they will call subjects on their cell phone if they have not received a call from them within 15 minutes. Subjects will be instructed to treat symptomatic hypoglycemia or confirmed BG level < 70 mg/dL with 15-30 grams of rapid-acting carbohydrate (such as juice or glucose tabs), re-check BG level in 15 minutes, and repeat as necessary until BG level is over 70 mg/dL. Study staff will advise subject/caregiver whether to continue current diabetes management or exit closed-loop control, as per the Treatment Protocol (Table 1).

7) Stopping Criteria

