If an individual subject has two episodes of a confirmed $BG < 50$ mg/dL (separated by at least 30 minutes), blood ketones > 1.0 mmol/L for over 2 hours, or any blood ketone level > 3.0 mmol/L, then the study will be stopped for that subject. Recall that subject will test for ketones after a confirmed $BG \geq 300$ mg/dL following CGM readings ≥ 300 mg/dL for > 1 hour. If any subject has a seizure, loss of consciousness or ketoacidosis ($CO_2 < 15$ mEq/L, or $pH < 7.3$) the study will be stopped for that subject and no additional subjects will be enrolled until the DSMB reviews the data.

If for any subject the $BG \geq 300$ mg/dL and blood ketones are > 1.0 mmol/L, the closed-loop control will be temporarily stopped, the infusion site will be changed, and supplemental insulin may be given at the discretion of the investigator. The closed-loop control will be restarted if $BG < 250$ mg/dL and blood ketones < 0.6 mmol/L.

If for any subject the $BG \geq 400$ mg/dL for any ketone levels, the closed-loop control will also be temporarily stopped, the infusion site will be changed, and supplemental insulin may be given if the investigator concludes that the issue is related to a site failure and not due to malfunction of the controller. The closed-loop control will be restarted if $BG < 250$ mg/dL and blood ketones < 0.6 mmol/L.

Additional information is shown in the Treatment Protocol table.

8) Treatment Protocol Table

Table 1. Hypoglycemia and hyperglycemia monitoring and treatment procedures.

Meter BG (mg/dL)	Ketones (mmol/L)	Clinical State	Action	Monitoring
Any		Seizure, loss of consciousness, or inability to consume oral treatment	STOP system Treat with SQ glucagon Notify MD/NP End closed-loop STOP study for this patient	Repeat BG every 15 minutes until $BG \geq 70\text{mg/dL}$
<70		Conscious, well-appearing	Treat with oral glucose Notify MD/NP Repeat MBG Continue closed-loop	Repeat BG every 15 minutes until $BG \geq 70\text{mg/dL}$
70-299		Asymptomatic and well	Continue closed-loop	Check BG (Premeal, pre and post exercise and midnight)
300-399	≤ 1.0	Asymptomatic and well	Continue with closed-loop Notify MD/NP May consider supplemental insulin	Repeat BG and ketones in 1 hour
300-399	> 1.0	Asymptomatic and well	Notify MD/NP SQ insulin correction, set change Suspend closed-loop May restart if $BG 80-250\text{ mg/dL}$ and ketones $< 0.6\text{ mmol/L}$. Encourage oral fluid intake.	Repeat BG and ketones in 1 hour

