Automated Insulin Delivery Device Acceptance	INSPIRE AID Acceptance (Draft) – Teen
PARENT OF YOUTH W T1D SURVEYS	
Fear of hypoglycemia	Hypoglycemia Fear Survey – Parent version
Diabetes burnout/burden	Problem Areas in Diabetes – Parent version
Quality of life–diabetes specific	Pediatric QoL Inventory (PedsQL) – Diabetes Module (8-12)– Parent version
Quality of life–diabetes specific	Pediatric QoL Inventory (PedsQL) – Diabetes Module (13-18) – Parent version

CONSTRUCT:	MEASURE:
Automated Insulin Delivery Device Acceptance	INSPIRE AID Acceptance (Draft) – Parent Version
ALL AGES	
Technology Acceptance	Comfort and Use of Technology Survey
Glucose Monitoring Satisfaction	The Glucose Monitoring Satisfaction Survey (GMSS)

6. Data Analysis

a. Primary Endpoint

The primary endpoint for the short-duration hotel study is safety, as defined as: 1) no more than one confirmed $BG < 50$ mg/dL; 2) no more than two confirmed $BG \geq 300$ mg/dL longer than 2 hours, unless determined to be from an infusion site failure; 3) no $BG \geq 400$ mg/dL; 4) no blood ketone level > 1.0 mmol/l for longer than 2 hours, or any ketone level > 3.0 mmol/L, unless determined to be from an infusion site failure; and 5) no significant adverse events, such as severe hypoglycemia (seizure, loss of consciousness), diabetic ketoacidosis.

b. Secondary Endpoints

Efficacy endpoints of interest will include:

- a. Mean meter and sensor glucose
- b. % Time in range (70-180 mg/dL)
- c. % Time below range (<70 mg/dL)
- d. % Time above range (>180 mg/dL)
- e. % Time in hypoglycemia (<60 mg/dL)
- f. % Time in hyperglycemia (>250 mg/dL)
- g. % time AP system active

The glycemic metrics will be calculated by total 24-hour period, and also broken down into daytime (6AM-11PM) and nighttime (11PM-6AM) periods.

c. Stopping

If an individual subject has two episodes of a confirmed $BG < 50$ mg/dL (separated by at least 30 minutes), blood ketones > 1.0 mmol/L for over 2 hours, or any blood ketone level > 3.0 mmol/L, then the study will be stopped for that subject. If any subject has a seizure, loss of consciousness or ketoacidosis ($CO_2 < 15$ mEq/L, or $pH < 7.3$) the study will be stopped for that subject and no additional subjects will be enrolled until the DSMB reviews the data.

d. Continuation

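### Ascertainment of the high-glucose part of the primary safety endpoint is incomplete, and untested time counts as event-free

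*Combined protocol and SAP*

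**What the plan says.** Section 6.a defines the primary safety endpoint by five components. Three concern the high side:

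- Component 2: "no more than two confirmed $BG \geq 300$ mg/dL longer than 2 hours", with an exception for infusion site failure.
- Component 3: "no $BG \geq 400$ mg/dL", with no minimum duration and no exception.
- Component 4: "no blood ketone level > 1.0 mmol/l for longer than 2 hours", nor any value above 3.0 mmol/L, again with the site-failure exception.

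CGM is not named in these components. The protocol uses BG for meter values (Table 1 is headed by meter BG) and speaks separately of CGM or sensor readings.

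High-side meter values have two sources. The first is a schedule: "Check BG (Premeal, pre and post exercise and midnight" (Table 1). Section 5.b.2 adds that staff do the midnight check, and section 5.b.3 requires the exercise checks of all subjects. The second is a rule in section 5.b.5: once CGM has been at 300 mg/dL or more for over an hour, "subject will test BG, and if confirmed BG" is again at least 300, ketones are tested. Section 5.b.7 repeats the ketone rule ("Recall that subject will test for ketones after a confirmed" meter value of that size). After a high meter value, Table 1 has BG and ketones repeated in one hour.

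Section 5.b.6 describes SMS "alerts on their cell phones for low sensor readings, or for other operational issues". It describes no alert for high readings. In section 6.b the highest glucose threshold is percent time above 250 mg/dL.

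**The concern.** Component 3 is breached by a single value of any duration, but the unscheduled test that could reveal it is required only after more than an hour at 300 mg/dL or above. The low side is treated differently: any CGM reading under 70 mg/dL calls for a meter test, and low readings generate a text alert.

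The plan does not say how untested time is handled. Under components worded as the absence of a value, an excursion that nobody measures is the same as no excursion. Incomplete detection can therefore only improve the reported result for components 2 to 4, and safety is the primary endpoint.

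**Working it through.** The plan states no event rate, detection rate or sample size calculation, so there is no figure to reproduce. The check traces each high-side component to the tests that could reveal it.

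**Component 2 (300 mg/dL or more for over 2 h).** The CGM trigger (over 1 h) is shorter than the endpoint duration (over 2 h). A qualifying excursion should prompt a test, day or night, if the sensor agrees and someone acts on it. Coverage is largely adequate. One loose end is that the start of the 2 h clock is not defined. If it starts at the first meter value, taken about 1 h after CGM onset, the excursion must last about 1 + 2 = 3 h to be documented.

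**Component 3 (any value of 400 mg/dL or more).** A peak with CGM at 300 or above for an hour or less meets no trigger. It is seen only if it coincides with a scheduled test. As an illustration, assume six scheduled tests a day (08:00, 12:00, 15:00, 16:00, 18:00, 24:00) and a randomly timed peak of L hours, with L no more than 1:

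P(peak meets a scheduled test) = 6 × L / 24

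- L = 0.25 h: 6.25%, about 6%
- L = 0.5 h: 12.5%, about 13%
- L = 1 h: 25%

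The longest gap under these times is 8 h, from midnight to breakfast. With breakfast 6 to 8 h after midnight, two nights give 12 to 16 h without a scheduled meter test: 12/60 = 20.0% to 16/60 = 26.7% of 60 h.

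**Component 4 (ketones).** No routine ketone test is scheduled. Every initial ketone test described depends on a meter value of 300 mg/dL or more. A ketone rise with meter BG below 300, or with no meter test, is not measured.

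**Section 6.b as a backstop.** Thirty minutes at 400 mg/dL adds 0.5/60 = 0.8% to time above 250 mg/dL. Thirty minutes at 260 mg/dL adds the same. The metric does not separate them and carries no run length.

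**Effect on what is observed.** Let p be the true proportion of children with a violation, s the probability that it is detected, and n the cohort size (8 to 16, section 4.e). Then

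P(no violation observed) = (1 − p·s)^n

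The values of p and s are assumptions:

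| n | p | s = 1.0 | s = 0.75 | s = 0.5 |
|---|---|---|---|---|
| 8 | 0.10 | 0.43 | 0.54 | 0.66 |
| 8 | 0.20 | 0.17 | 0.27 | 0.43 |
| 8 | 0.30 | 0.06 | 0.13 | 0.27 |
| 16 | 0.10 | 0.19 | 0.29 | 0.44 |
| 16 | 0.20 | 0.03 | 0.07 | 0.19 |
| 16 | 0.30 | 0.003 | 0.02 | 0.07 |

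For 8 children and p = 0.20, halving detection raises the chance of a clean record from 0.17 to 0.43.

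**Link to progression.** Section 6.d moves to the next age group if the stopping criteria are not met and the DSMB agrees. Of the high-side components, only the ketone limits appear in the section 6.c criteria. An unseen high can matter there because it also means no ketone test.

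**The case against.** The strongest reply is that this is a closely watched feasibility study. Scheduled meter tests need no trigger, the CGM rule is written into the protocol and has no night exemption, children are supervised throughout, and staff are at the hotel each night. Sensor values above 300 or 400 mg/dL already count in time above 250 mg/dL, which is reported separately for the night. The documents are silent on the sensor's own alarms, so the lack of a text alert does not show that nobody would notice.

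Much of this stands, and it rules out several stronger readings:

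- A reader might infer that highs are seen only when a test happens to be triggered. The scheduled tests and the CGM rule contradict that.
- A reader might infer that the high-side components are unobserved overnight. The CGM rule still applies then, and an excursion that lasts until breakfast meets the premeal test.
- A reader might take 20% to 27% as the share of events missed. It is time without a scheduled meter test under an assumed breakfast hour.

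The reply does not cover short peaks of 400 mg/dL or more between tests, CGM triggers that are not acted on, or ketone rises at meter BG below 300. Nor does it give the reader of the results a way to tell how often these occurred.

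**Conclusion.** The point holds in a limited form. Ascertainment is incomplete for component 3, conditional on a high meter value for component 4, and largely adequate for component 2 if the CGM rule is followed. The resulting error runs one way, toward a better safety result. Its size cannot be computed from the documents. The 6% to 25% chance of a scheduled test catching a short peak rests on assumed test times and random timing, and the cohort probabilities rest on assumed p and s.

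It would be tempting to conclude that a cohort can pass because excursions went untested. The documents do not support that. Section 6.a sets no cohort-level pass rule, and progression rests on the stopping criteria plus DSMB agreement. Untested glucose affects the reported endpoint directly and progression only through the ketone limits. This is a cheap improvement to the analysis and does not invalidate the design.

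**What to change.** Add a supporting analysis to section 6, using the CGM data already uploaded at the end of the visit (section 5.b.9). For each child, beside the meter-based primary endpoint, report:

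- (a) any CGM run at 300 mg/dL or more lasting over 2 h;
- (b) any CGM reading at 400 mg/dL or more, or at the sensor's upper reporting limit (the documents give no limit, so it must be stated);
- (c) the number of CGM triggers (300 mg/dL or more for over 1 h) and the proportion that received the required meter and ketone tests.

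Report and discuss disagreements with the meter-based result, but do not let the CGM version overrule it: sensor values are unconfirmed. CGM cannot recover ketones, so state that component 4 covers tested time only.

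Sections 5.b.5 and 5.b.7 tie ketone testing to the CGM trigger, while Table 1 classifies every meter value of 300 to 399 mg/dL by ketone level. These passages must be reconciled on whether a scheduled meter value of 300 mg/dL or more also calls for a ketone test.

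The cost is a little programming and no added testing. The downside is that sensor error may add some false events, which is why the analysis is supporting only.

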≥ 400	Any		Notify MD/NP SQ insulin correction, set change Suspend closed-loop May restart if the investigator concludes that the issue is related to a site failure and not due to malfunction of the controller, $BG 80-250\text{mg/dL}$ and ketones $< 0.6\text{ mmol/L}$. Encourage oral fluid intake.	Repeat BG and ketones in 1 hour
Any	>1.0 for $>2\text{h}$ or >3.0 once		STOP system Notify MD/NP SQ insulin correction, set change End closed-loop STOP study for this patient	Repeat BG and ketones in 1 hour

Any	Any	Abdominal pain, vomiting, altered level of consciousness	STOP system Notify MD/NP SQ insulin correction, set change End closed-loop STOP study for this patient Transfer to ER for further Tx	Per clinical scenario
-----	-----	--	---	-----------------------

9) End of Hotel Visit

At the conclusion of the hotel visit (afternoon of 3rd day), subjects will return to their usual pre-study insulin pump and regimen. Study devices will be returned and uploaded for data analysis. Subjects and parents will participate in semi-structured interviews and/or focus groups to give opinions about system usability, confidence in system safety, fear of hypoglycemia, and diabetes-related distress. Study staff will call subjects/parents approximately 24 hours after discharge to review BG control and assess for late adverse events.

10) Surveys and Interviews

Subjects and parents/caregivers will, at the conclusion of the hotel visit, complete several surveys/questionnaires to assess the effect of the closed-loop system on diabetes-related quality of life and distress, fear of hypoglycemia, and satisfaction with diabetes technology (see Table 2). Subjects and caregivers will also participate in focus groups or semi-structured interviews related to human factors issues, and perceived burdens and benefits, of the closed-loop system. Only the interviewer and participant(s) will be present during the interview/focus group.

Table 2. Surveys/questionnaires to assess effect of the closed-loop AP system.

CONSTRUCT:	MEASURE:
CHILD/ADOLESCENT SURVEYS	
Fear of hypoglycemia	Hypoglycemia Fear Survey
Diabetes burnout/burden	Problem Areas in Diabetes
Quality of life–diabetes specific	Pediatric QoL Inventory (PedsQL) – Diabetes Module (8-12)
Quality of life–diabetes specific	Pediatric QoL Inventory (PedsQL) – Diabetes Module (13-18)
Automated Insulin Delivery Device Acceptance	INSPIRE AID Acceptance (Draft) - Child

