If stopping criteria are NOT met for an age cohort, then after that cohort is completed we will proceed to next lower age cohort after DSMB review and approval. However, even if stopping criteria are not met, additional cohorts at a given age range may be enrolled at discretion of investigators if adjustments to algorithm tuning parameters are desired based on glycemic results and comparison with subjects' pre-study baseline glycemic profiles.

7. Financial Considerations

a. Subject compensation

Subjects/parents will receive \$50 for the enrollment visit and \$100/day for the hotel visit, for a maximum of \$350 compensation for participation.

b. Meal Stipend

All subject meals during the hotel stay will be covered by the study. Parents will receive \$75 per day stipend for their meals and expenses during the hotel stay. Parking at the hotel will be covered by the study.

8. Adverse Event Reporting and Safety Monitoring

a. Definition

Reportable adverse events in this study include any untoward medical occurrence that meets criteria for a serious adverse event or any medical occurrence (expected or unexpected) in a study participant that is study or device-related.

Hypoglycemic events are recorded as adverse events if the event required assistance of another person due to altered consciousness and required another person to actively administer carbohydrate, glucagon, or other resuscitative actions to prevent harm. This means that the subject was impaired cognitively to the point that he/she was unable to treat his or herself, was unable to verbalize his or her needs, was incoherent, disoriented, and/or combative, or experienced seizure or coma. These episodes may be associated with sufficient neuroglycopenia to induce seizure or coma. If glucose measurements are not available during such an event, neurological recovery attributable to the restoration of glucose to normal is considered sufficient evidence that the event was induced by a low plasma glucose concentration.

Hyperglycemic events are recorded as adverse events if the event involved diabetic ketoacidosis, as defined by the DCCT, and had all of the following:

- Symptoms such as polyuria, polydipsia, nausea, or vomiting;
- Serum ketones or large/moderate urine ketones;

- Either arterial blood pH <7.30 or venous pH <7.24 or serum bicarbonate <15; and
- Treatment provided in a health care facility

b. Recording of adverse events

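### For BG ≥400 mg/dL, Section 5.b.7 and Table 1 attach the site-failure conclusion to different actions, and Table 1's last row directs insulin with no BG limit

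*Combined protocol and SAP*

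**What the plan says.** **BG ≥400 mg/dL.** Section 5.b.7 (Stopping Criteria) suspends closed loop and changes the infusion site. It permits supplemental insulin if the investigator concludes that the site failed and the controller did not malfunction. Closed loop is then to be restarted at BG <250 mg/dL with ketones <0.6 mmol/L. Table 1 (Section 5.b.8) also suspends closed loop and changes the set, but it directs the insulin correction without any condition. It allows restart only if the investigator reaches that conclusion, BG is 80-250 mg/dL and ketones are <0.6 mmol/L.

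**Altered consciousness.** In Table 1's last row, both the BG and the ketone cells are set to Any. The clinical state is "Abdominal pain, vomiting, altered level of consciousness". After stopping the system and notifying the MD/NP, the action is "SQ insulin correction, set change End closed-loop STOP study for this patient Transfer to ER for further Tx". The row for BG <70 mg/dL applies to a child who is "Conscious, well-appearing", and its action is "Treat with oral glucose Notify MD/NP Repeat MBG Continue closed-loop". The first row, which leads to glucagon, requires "Seizure, loss of consciousness, or inability to consume oral treatment".

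**Body text on low BG.** For any documented BG <70 mg/dL, or symptoms of hypoglycemia, Section 5.b.5 says "subject will be treated with 15-30 gm rapid-acting carbohydrate (such as juice or glucose tabs), and BG will be rechecked in 15 minutes". Section 8.a records hypoglycemia as an adverse event where "the event required assistance of another person due to altered consciousness and required another person to actively administer carbohydrate, glucagon, or other resuscitative actions" were needed.

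**The concern.** These are action rules for children, stepping down to under 8 years, on an investigational insulin controller, in a trial whose primary endpoint is safety.

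At BG ≥400 mg/dL the key question is whether the controller caused the reading. The two texts use the answer for different purposes. If staff follow 5.b.7, a controller under suspicion goes back on once BG and ketones have recovered, and that paragraph makes no provision for insulin in a child who is severely hyperglycemic for that reason.

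In the last row, the three signs suggest suspected ketoacidosis, where insulin makes sense. But altered consciousness is also how Section 8.a describes hypoglycemia that needs help from another person, and there insulin would do harm. The row states no BG limit and asks for no BG reading before insulin.

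**Working it through.** No sample size, power or event figure is involved, so the check sets the texts side by side.

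**1. BG ≥400 mg/dL**

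| Investigator's conclusion | Action | Section 5.b.7, BG ≥400 paragraph | Table 1, ≥400 row |
|---|---|---|---|
| Site failure, not controller | Insulin | May be given | Directed |
| Site failure, not controller | Restart | BG <250 and ketones <0.6 | Allowed at BG 80-250 and ketones <0.6 |
| Controller malfunction suspected | Insulin | No provision | Directed |
| Controller malfunction suspected | Restart | BG <250 and ketones <0.6 | Not allowed |

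The texts part where the controller is suspected. Once BG is 80-249 mg/dL (whole numbers) and ketones are <0.6 mmol/L, 5.b.7 restarts and Table 1 does not. Applying the stricter rule would settle restart. It would not settle insulin, because the stricter text there is 5.b.7, which withholds it.

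Two smaller differences lie alongside:

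- Restart range: BG <250 against 80-250. They agree at 80-249 and differ below 80 and at exactly 250. Since BG <70 is treated under 5.b.5, the practical low-side gap is 70-79 mg/dL.
- BG 300-399 with ketones >1.0 mmol/L: the preceding paragraph of 5.b.7 leaves insulin to the investigator's discretion; Table 1 directs it.

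**2. The last row**

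Four of Table 1's eight rows direct an SQ insulin correction. Two carry a BG range (300-399 with ketones >1.0, and ≥400). Two have BG set to Any (the ketone-stop row and the last row).

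Now take a disoriented child with BG <70 mg/dL who can still swallow and has no ketone result:

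- Row 1 does not match: no seizure, no loss of consciousness, and oral treatment is possible.
- The <70 row does not match: the child is not well-appearing.
- The 70-299 row, both 300-399 rows and the ≥400 row do not match on BG.
- The ketone-stop row does not match without a ketone result.
- The last row matches if any one of its signs is enough, and it directs insulin. If all three signs are required (the cell has commas and no conjunction, whereas row 1 writes one), no row matches.

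On either reading, the number of Table 1 rows that give this child carbohydrate is 0 of 8. Section 5.b.5 does give it. On the natural reading, then, the last row contradicts the body text.

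**The case against.** The best defense is that the body text already protects the child. Section 5.b.5 applies to any BG <70 mg/dL with no requirement that the child look well, and 5.b.6 repeats the carbohydrate rule. Section 5.b.4 ties correction doses to hyperglycemia and staff instruction. In the last row the MD/NP is notified before insulin is mentioned, and Section 5.b.2 keeps every subject under direct supervision. A child who cannot take oral treatment falls under row 1. All of this stands. A reader might infer that the plan would have a hypoglycemic child given insulin and left without carbohydrate. The documents do not support that: staff would have to give a hyperglycemia correction at a known low BG, against 5.b.5.

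On BG ≥400, the defense is that the 5.b.7 wording on insulin is permissive, that the section refers the reader on to Table 1, and that 5.b.5 makes Table 1 the reference for insulin and continuation when ketones exceed 1.0 mmol/L. The preceding 5.b.7 paragraph, which starts at BG ≥300 with ketones >1.0, also leaves insulin open there. So the insulin gap is clearest at BG ≥400 with ketones ≤1.0. But the reference to Table 1 is only for additional information. It does not say which text governs where they differ, and nothing in 5.b.7 withdraws its restart rule. Nor are the two texts giving opposite orders, as a reader might conclude: they attach one condition to different actions.

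The ketone-stop row ("STOP system Notify MD/NP SQ insulin correction, set change End closed-loop STOP study for this patient", BG set to Any) might look like an equal hazard. It is much weaker. Ketones are first tested after a confirmed BG ≥300 mg/dL, so reaching BG <70 would need a fall of more than 300 − 70 = 230 mg/dL with ketones still elevated. Its overlap with the <70 row on continuing closed loop is settled by 5.b.7 and 6.c, which both stop the study for that subject.

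**Conclusion.** Both parts are wrong as written and should be fixed. For BG ≥400 mg/dL, the two texts disagree on insulin and on restart whenever a controller malfunction is suspected, and neither is said to prevail. In Table 1's last row, insulin is directed with no BG limit for a sign that the protocol itself also associates with hypoglycemia, against 5.b.5.

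The size is limited. The documents give no event rates, so frequency cannot be estimated, and the written safeguards make the worst outcome in the last row unlikely. A reader might infer that the trial is unsafe to run until this is corrected; the documents do not support that, given those safeguards. The point concerns how staff act, not the definition of any endpoint. It assumes that the last row means any one of its signs (if all three are required, the fault is a gap in the table instead) and that no other operating instruction, absent from these documents, says which text governs.

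**What to change.** **Section 5.b.7, BG ≥400 paragraph.** Match Table 1: insulin does not depend on the cause, and closed loop may restart only if the investigator concludes site failure and not controller malfunction, BG is 80-250 mg/dL and ketones are <0.6 mmol/L. Table 1's ≥400 row already reads this way and stays as it is.

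**Section 5.b.7, preceding paragraph (BG ≥300 with ketones >1.0).** Use the same 80-250 mg/dL restart range, and align its discretionary insulin with Table 1's directed insulin.

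**Table 1, last row.** Keep stopping the system, MD/NP notification and ER transfer. Require a meter BG first and give no insulin at BG <70 mg/dL. Send BG <70 with altered consciousness to hypoglycemia treatment: oral carbohydrate if the child can swallow, otherwise the row 1 glucagon. The BG or ketone level above which insulin is given is for the study clinicians and the DSMB to set.

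**Optional tidying.** Apply the same BG <70 exclusion to the ketone-stop row, and add to Table 1 the stop after two confirmed BG <50 mg/dL that 5.b.7 and 6.c already state.

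Cost: a text amendment to two paragraphs and one table row. It adds no subjects or visits, and the meter check uses the study meter already in hand. Section 6.c needs no change.

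### Table 1's last row orders insulin correction for altered consciousness with no glucose condition, so at BG <70 mg/dL it can contradict the carbohydrate order in 5.b.5 and 5.b.6

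*Combined protocol and SAP*

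**What the plan says.** Table 1 in section 5.b.8 of the combined protocol and SAP sets out actions by meter glucose, ketones and clinical state. Three of its rows matter here.

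- **Last row.** Glucose and ketones are both Any. The clinical state is "Abdominal pain, vomiting, altered level of consciousness" and the action is "STOP system Notify MD/NP SQ insulin correction, set change End closed-loop STOP study for this patient Transfer to ER for further Tx". Monitoring is left to the clinical scenario.
- **The <70 row.** The clinical state is "Conscious, well-appearing" and the action is "Treat with oral glucose Notify MD/NP Repeat MBG Continue closed-loop".
- **First row.** Glucose is Any, the clinical state is "Seizure, loss of consciousness, or inability to consume oral treatment", and the treatment is glucagon. Its monitoring cell begins "Repeat BG every 15 minutes until" and ends at a BG of at least 70 mg/dL.

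The text gives its own order for low glucose. Section 5.b.5 says: "For any documented BG <70 mg/dL or in the setting of symptoms of hypoglycemia", staff are alerted and "subject will be treated with 15-30 gm rapid-acting carbohydrate", with a recheck after 15 minutes. Section 5.b.6 repeats the carbohydrate order for symptomatic hypoglycemia or a confirmed BG below 70 mg/dL. Section 5.b.7 points to the table only for additional information. No sentence says whether the table or the text prevails where they differ.

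**The concern.** Altered consciousness can be a sign of low glucose as well as of ketoacidosis. Section 8.a recognises this: its definition of a reportable hypoglycemic event includes a child who is incoherent, disoriented or combative, short of seizure or coma. The same sign in Table 1 leads to insulin, and nothing in that row requires a glucose reading first. Insulin and carbohydrate are opposite treatments for a child with BG below 70 mg/dL, and insulin would deepen the low.

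A treatment table is what staff reach for in an emergency. The study plans cohorts down to children under 8 years, and the introduction itself stresses young children's sensitivity to insulin and their limited ability to report symptoms.

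**Working it through.** No formula applies and the plan gives no figure to reproduce. The check lists what each row orders and then matches a child with BG <70 mg/dL to the rows.

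**Step 1: rows of Table 1, in order**

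| Row | Glucose (mg/dL) | Ketones (mmol/L) or clinical state | Treatment ordered |
|---|---|---|---|
| 1 | Any | seizure, unconscious, or cannot take oral treatment | glucagon |
| 2 | <70 | conscious and well | oral glucose |
| 3 | 70-299 | well | none |
| 4 | 300-399 | ketones ≤1.0, well | insulin may be considered |
| 5 | 300-399 | ketones >1.0, well | insulin correction |
| 6 | ≥400 | any ketones | insulin correction |
| 7 | Any | ketones >1.0 for >2 h, or >3.0 once | insulin correction |
| 8 | Any | any ketones; abdominal pain, vomiting, altered consciousness | insulin correction |

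Insulin correction is ordered in rows 5, 6, 7 and 8, which is 4 of 8. Rows 5 and 6 carry a glucose floor (2 of 4); rows 7 and 8 do not (2 of 4). Row 8 alone has no ketone condition either. Rows 1, 2, 7 and 8 can apply below 70 mg/dL: 2 order insulin, 1 glucagon and 1 oral glucose. By comparison, both supplemental-insulin statements in 5.b.7 carry a floor (≥300 and ≥400 mg/dL) and are permissive.

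**Step 2: a child with BG <70 mg/dL, by clinical state**

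- *Conscious and well.* Row 2 gives oral glucose, in agreement with 5.b.5 and 5.b.6.
- *Shaky or sweating, but not confused, vomiting or in abdominal pain.* No row matches on clinical state. The text orders carbohydrate. This is a gap in the table.
- *Confused, able to swallow.* Row 1 does not match, because the child is conscious, is not seizing and can take oral treatment. Row 2 does not match, because the child is not well. If one sign is enough, row 8 is the only match on clinical state and it orders insulin, against the carbohydrate order in the text. If all three signs are needed, no row matches and the text alone applies.
- *Vomiting, unable to take oral treatment.* Row 1 orders glucagon. If one sign is enough, row 8 also matches and orders insulin. No precedence is stated.

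**Step 3: does the all-three reading clear row 8?** It removes the contradiction for the child who is only confused. It does not add a glucose condition: a child with all three signs and BG <70 mg/dL would still fall under the insulin order.

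**The case against.** The strongest reply is that the last row is plainly a ketoacidosis row. Its signs fit that picture, section 5.b.4 ties correction doses to hyperglycemia, and the MD/NP is notified before insulin in the row's own list of actions. Children are supervised at all times, and 5.b.5 requires a meter reading for symptoms of hypoglycemia. On this view, harm needs a clinician to see a low value, set aside 5.b.5 and correct it with insulin. The reply adds that the first row joins its signs with an explicit *or* while the last row does not, so the last row may describe one combined picture. It also notes that 5.b.5 and 5.b.6 refer to Table 1 for limited purposes (ketone-related insulin, site change, continuing or leaving closed loop) and do not hand the carbohydrate order over to it.

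Much of this stands. It makes harm less likely, and it means the contradiction for the confused child depends on how the list of signs is read. It does not supply the missing glucose condition. Notification and insulin sit in one action list, and nothing makes insulin wait for a reading or a decision.

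A reader might go further in three ways that the documents do not support:

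- That the <70 row itself conflicts with 5.b.5 and 5.b.6. It is silent on a symptomatic child, and the text fills the gap.
- That the ketone row is an equal hazard. Ketones are routinely tested only after a confirmed BG ≥300 mg/dL, so meeting that row below 70 mg/dL is unlikely.
- That insulin in the last row should require both high glucose and raised ketones. That would contradict the ≥400 row, which orders insulin at any ketone level.

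**Conclusion.** Wrong as written, on patient safety. The insulin order in the last row has no glucose condition and is the wrong instruction at BG <70 mg/dL. If one sign is enough, which is the more natural reading of the list, the table contradicts 5.b.5 and 5.b.6 for a confused child who can swallow. If all three are required, the table has no row for that child and the text alone covers the case.

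The size is one row of eight with neither a glucose nor a ketone condition on insulin. This is a count of written orders. The documents give no rate for the situation, so a reader should not infer that harm is probable or that staff would in fact give insulin to a child with a known low. The conclusion assumes only that the table may be followed as it stands in an emergency. Sample size, endpoints and analysis are not affected.

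**What to change.** 1. **Last row.** Keep the system stop, MD/NP notification, study stop and ER transfer. Require a meter glucose first. Give no insulin at BG <70 mg/dL. Otherwise give insulin only as the glucose and ketone limits in the table's other rows direct, with any further cut-off set by the study clinicians. Because the 300-399 rows are labelled for a well child, say that it is their glucose and ketone limits that carry over.
2. **The <70 row.** Extend it, or add a row, for a symptomatic or confused child who can swallow: 15-30 g carbohydrate, notify MD/NP, recheck BG in 15 minutes, no insulin. This closes a gap and brings the table into line with 5.b.5 and 5.b.6.
3. **Precedence.** State that at BG <70 mg/dL, or in suspected hypoglycemia when BG cannot be measured at once, the first row (glucagon) takes precedence over the last row. The second clause keeps the meter check from delaying glucagon.
4. **Optional and minor.** Add the same BG <70 exclusion to the ketone row.

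The cost is protocol wording and at most one added table row. The one practical downside is a glucose reading before insulin is given.
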